Executive Functioning (intermediary target) will be assessed using multiple measures. The Delis-Kaplan Executive Function System (D-KEFS)⁶⁵ was specifically designed to detect deficits in high-level cognitive functions, such as from mild brain damage to the frontal lobe⁸⁴ and has demonstrated strong reliability and validity in various clinical populations. We will administer five tests from the D-KEFS that examine components of executive functioning, such as inhibition (the Color-Word Interference Test), cognitive flexibility or switching (Verbal Fluency, Trails Tests, Design Fluency) and Planning (Towers). The Penn Conditional Exclusion Test (PCET)⁸⁵ will be used as a measure of executive functioning in which Veteran participants must perform a computerized sorting task with three shifting sorting principles. The PCET is similar to the Wisconsin Card Sorting Test⁸⁶, a classic test of executive functioning, but it has four alternate test versions that can be administered with comparable validity and reliability, better allowing for repeated testing over time.

Table 2. Assessments and Timeline									
Measure	Baseline	Session 7	Session 13	Session 21	Post Assessment (After Session 26)	3-Month Follow- up	6- Month Follow- up		
Diagnostic Assessment									
Structured Interview for Hoarding Disorder (SIHD)	х								
Mini-International Neuropsychiatric Exam (MINI)	х								
Hoarding severity (Primary Outcome)									
Savings Inventory-Revised (SI-R)	х	х	х	х	Х	х	х		
Functional Capacity (Secondary Outcome)									
UCSD Performance-Based Skills Assessment (UPSA)	x	х	х	х	x	х	х		
UCSD SORT Test (U-SORT)	х	х	х	х	Х	х	х		
Self-Reported Functioning (Secondary Outcome)									
Specific Levels of Functioning test (SLOF)	х	х	х	х	Х	х	х		
World Health Organization Disability Assessment Schedule (WHODAS 2.0)	x	х	х	х	х	х	х		
Quality of Life (secondary outcome)									
Quality of Life in Neurological Disorders (Neuro-QoL)	х	х	х	х	Х	х	х		
Executive Functioning (Intermediary Target)									
Delis-Kaplan Executive Function System (D-KEFS) Color-Word Interference, Verbal Fluency, Trails Tests, Design Fluency, Towers	x	x			x	x	x		
Penn Conditional Exclusion Test (PCET)	х	х			х	х	х		
Avoidance (Intermediary Target)	·				•				
Behavioral Avoidance Test (BAT)	х	х	х	х	х	х	х		
Acceptance and Action Questionnaire 2 (AAQ-2)	Х	Х	Х	Х	х	х	х		

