- Statistical Analysis: The dependent variable will be analyzed by mixed effects model methods as described above. Baseline demographic and other clinically important characteristics at baseline will be assessed for imbalance between the two groups and their association with the outcome using a univariate analysis. Those found to be significantly unbalanced between intervention groups (p < 0.10) and moderately associated with the outcome (p < 0.15) will be included as covariates in the model. We will adjust p-values for multiple testing within each hypothesis separately by using a Bonferroni correction whenever more than one variable is being tested

Hypotheses 2.1: Treatment adherence, improvement in executive functioning, and reduction in avoidance will mediate hoarding symptom reduction in CREST.

Dependent Variables: Hoarding severity (SI-R)

Independent Variables: Executive Functioning (D-KEFS scaled scores and PCET), Avoidance (AAQ and BAT) and Treatment Adherence score.

Statistical Analysis: The effect of mediator variables will be tested following the procedures recommended by Kraemer⁹⁴, Bauman⁹⁵, Cohen and Cohen⁹⁶, and Busemeyer and Jones⁹⁷. Briefly, treatment mediators explain how or why one variable affects the treatment effect and are defined as mechanisms through which a treatment might achieve its effects. The mediator's effect is measured during the treatment and is correlated with treatment choice and may possibly be a result of treatment and have either a main or interactive effect on the outcome. The dependent or outcome measure (SI-R) will be evaluated throughout the study and will be used as a repeated measure for all the available time points. In essence, the slope of each outcome measure on time will be used as a dependent measure. The mediator and bootstrap technique will be used to calculate a 95% confidence interval for mediation effect. Random effects models will be used for analysis and the change score of mediators will be included in the model.

Hypotheses 2.2: Symptom severity reduction and improved functional capacity will mediate improved quality of life in CREST.

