Dependent Variables: Hoarding severity (SI-R), Functioning (UPSA, USORT, SLOF, WHODAS 2.0) Independent Variables: Quality of life (Neuro-QoL) Statistical Analysis: The effect of mediator variables will be tested similar to the hypothesis 2.1. **Exploratory Aim 3:** To explore **age and baseline executive functioning** as moderators in order to determine subpopulations in which CREST work best. **Exploratory Aim 4:** To examine time to **maximum effect of treatment gains**.

These aims are focused on exploring on whom and under what conditions the treatment works best. These analyses may identify subpopulations with possibly different mechanisms and must be a baseline or prerandomization characteristic that could impact treatment outcome. We will focus on the moderator effect of age and baseline executive functioning and their interactions with treatment group. Age will be explored as continuous and ordinal (i.e. 45-55, 56-65, 66-75, 76-85) in format. If the interaction effect is significant, pairwise comparisons of groups will be performed. These analyses will examine interactions of group with time at each level of the moderator, and evaluate treatment within each moderator subgroup. These exploratory aims will be examined using random effects regression analyses for each candidate moderator as a main effect and in interaction, similarly to methodology used for the hypothesis testing. Furthermore, we will explore time to maximum effect of treatment gains (>35% reduction on SI-R) using survival analysis. The estimated survivorship curves will be obtained from Kaplan-Meier maximum likelihood estimates for each treatment group. The parameter estimates and 95% CI for the hazard ratio will be obtained from the Cox proportional hazards. Subjects who do not respond to treatment will be censored on their last visit date.

Power Analysis

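### The variable listing for Hypothesis 2.2 reverses the hypothesis: quality of life is the mediated outcome in the sentence but the independent variable in the listing

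*Combined protocol and SAP*

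**What the plan says.** All of this is in the combined protocol and SAP, under Statistical Plan.

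- **Hypothesis 2.2, sentence:** "Symptom severity reduction and improved functional capacity will mediate improved quality of life in CREST".
- **Hypothesis 2.2, listing:** "Dependent Variables: Hoarding severity (SI-R), Functioning (UPSA, USORT, SLOF, WHODAS 2.0) Independent Variables: Quality of life (Neuro-QoL").
- **Hypothesis 2.2, method:** "The effect of mediator variables will be tested similar to the hypothesis 2.1". No other model is given.
- **Hypothesis 2.1, the method adopted:** SI-R is the dependent variable, and the proposed mediators are listed as "Independent Variables: Executive Functioning (D-KEFS scaled scores and PCET), Avoidance (AAQ and BAT) and Treatment Adherence score". The text then says "The dependent or outcome measure (SI-R) will be evaluated throughout the study", "In essence, the slope of each outcome measure on time will be used as a dependent measure" and "Random effects models will be used for analysis and the change score of mediators will be included in the model". A bootstrap 95% confidence interval is planned for the mediation effect.

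The Measures section assigns two instruments to functional capacity, UPSA and U-SORT. It places SLOF and WHODAS 2.0 under self-reported functioning.

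**The concern.** A mediation analysis is defined by which variable is the outcome and which lies on the path to it. The sentence and the listing for Hypothesis 2.2 give opposite answers, and the method line, which only points back to Hypothesis 2.1, does not choose between them.

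An analyst who programs from the listing would estimate the path treatment → quality of life → symptoms and functioning. The bootstrap interval would then describe an indirect effect on SI-R or on a functioning scale, whereas the hypothesis concerns an indirect effect on Neuro-QoL. The output need not reveal the mistake: if the measures move together, the reversed model can also give a non-zero indirect effect. With both directions in the plan, either model could later be presented as the prespecified one.

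**Working it through.** The plan gives no figure to reproduce here. The check sets the texts side by side and counts.

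**1. Role of each measure under the two texts**

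| Measure | Domain in Measures section | Role in the sentence | Role in the listing |
|---|---|---|---|
| Neuro-QoL | Quality of life | Outcome | Independent |
| SI-R | Hoarding severity | Mediator | Dependent |
| UPSA | Functional capacity | Mediator | Dependent |
| U-SORT | Functional capacity | Mediator | Dependent |
| SLOF | Self-reported functioning | Not named | Dependent |
| WHODAS 2.0 | Self-reported functioning | Not named | Dependent |

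All 4 measures covered by the sentence have the opposite role in the listing. The other 2 are not functional capacity as the Measures section uses the term.

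**2. How the plan uses the labels elsewhere**

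- Hypotheses 1.1-1.3: treatment group and time are independent; the outcomes, Neuro-QoL among them, are dependent.
- Hypothesis 2.1: the mediated outcome (SI-R) is dependent; the mediators are independent.

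Only Hypothesis 2.2 departs from this convention.

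**3. The Hypothesis 2.1 method applied to each text**

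The plan writes no equation. I assume that treatment group is the exposure, that the listed independent variable takes the mediator's place as in Hypothesis 2.1, that each dependent variable has its own model, and that the indirect effect is the product of a (group → change in mediator) and b (change in mediator → outcome slope, given group).

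- *Sentence:* the outcome is the Neuro-QoL slope. For each mediator k, the indirect effect is a(k) × b(k), where a(k) is the group effect on change in SI-R, UPSA or U-SORT. Count: 1 outcome × 3 mediators = 3 effects, or 1 × 5 = 5 if functioning overall is meant.
- *Listing:* the outcomes are the slopes of SI-R, UPSA, U-SORT, SLOF and WHODAS 2.0. For each outcome j, the indirect effect is a × b(j), where a is the group effect on change in Neuro-QoL. Count: 5 outcomes × 1 mediator = 5 effects.
- *Effects common to both:* 0. The two sets use different a paths and different outcomes, so estimates from one do not supply the other.

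**4. Does anything else settle the direction?**

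- *Visit timing:* Table 2 marks SI-R, UPSA, U-SORT, SLOF, WHODAS 2.0 and "Quality of Life in Neurological Disorders (Neuro-QoL") at 7 of 7 visits each. No measure precedes another by design.
- *The plan's definition of a mediator:* it must be measured during treatment. Neuro-QoL meets that as well as the others do.
- *Treatment-to-mediator step:* SI-R and functioning would be dependent variables in that step, but the independent variable would then be treatment group, not Neuro-QoL. Neuro-QoL would still have to be dependent in the outcome step, and the listing never gives it that role.

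**5. Size of the mediator set**

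The plan applies a Bonferroni correction within each hypothesis when more than one variable is tested. If mediators are tested one at a time, the set matters: 0.05 / 3 = 0.0167 with SI-R, UPSA and U-SORT; 0.05 / 5 = 0.010 with SLOF and WHODAS 2.0 added.

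**The case against.** The strongest reply is that this is an evident slip. The hypothesis sentence is unambiguous, it stands immediately above the listing, and it is the only text that says which variables mediate; the listing never uses that word. Read with Hypothesis 2.1 as a template, it tells a careful analyst what to do. The count of five reversed effects also rests on readings: that the listed independent variable takes the mediator's place, that treatment group is the exposure (neither mediation listing names it), and that each dependent variable has its own model. The words limiting the hypothesis to CREST also leave open whether mediation is assessed within that arm or between arms. Finally, the functioning list is the same four instruments as in Hypotheses 1.1-1.3, so functional capacity may simply be loose wording for functioning.

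Much of this stands. The intended direction is hardly in doubt, harm arises only if the listing is followed, and the mismatch over SLOF and WHODAS 2.0 is minor. It does not remove the contradiction. The listing is the line most likely to be turned into code, nothing in the document corrects it, and Hypothesis 2.2 is a numbered hypothesis, separate from the aims labelled exploratory.

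**Conclusion.** The concern holds. As written, the listing specifies the reverse of the stated hypothesis: 4 of 4 measures covered by the sentence have their roles exchanged, and 0 of the 5 indirect effects that follow from the listing are the one hypothesised. The role reversal is read directly from the text; the count of five depends on the modelling assumptions set out in the check.

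The scope is Hypothesis 2.2 alone. The primary SI-R comparison, the tests under Hypotheses 1.1-1.3, Hypothesis 2.1 and the sample size of 136 are untouched. No effect on estimates or power can be given, because the document reports neither an arm effect on Neuro-QoL nor its correlation with the other measures. The error is probably clerical, but it should be corrected before the mediation analysis is programmed.

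**What to change.** - **Roles:** in the Hypothesis 2.2 listing, make Neuro-QoL the dependent variable and the changes in SI-R and the functioning measures the independent (mediator) variables, matching Hypothesis 2.1.
- **Mediator set:** in the same edit, either limit the functioning mediators to UPSA and U-SORT, or reword the sentence to refer to functioning overall and keep SLOF and WHODAS 2.0.
- **Exposure:** name treatment group as the exposure. This is a clarification beyond the reversal itself, since the Hypothesis 2.1 listing omits it too.

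The cost is two edited lines, plus a few words in the sentence if the self-report scales stay. No data collection changes, because Table 2 already schedules all six measures at all seven visits.

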Cognitive Rehabilitation and Exposure Therapy for Veterans with Hoarding Disorder

NCT02402647

February 1, 2023

Current Proposal

Proposed Study Design

The proposed study includes a 26-session controlled, randomized clinical trial designed to test the hypothesis that while targeting avoidance produces changes in HD symptoms, targeting executive dysfunction as well as avoidance will lead to even greater symptomatic changes, and secondarily in functioning and quality of life. Further, we will explore outcome moderators (age and baseline executive functioning) and time to maximum effect. To do this, we will compare CREST (CCT + ET) to ET alone. The study will be comprised of 4 phases (see Figure 2) (1) Pre-Treatment Evaluation Phase (1 assessment); (2) During Treatment Evaluation Phase (3 assessments; at sessions 7, 13, and 21); (3) End of Treatment (1 assessment after session 26); and 4) 3 and 6-month Follow-up Phase (2 assessments).

Patient Inclusion/Exclusion

The inclusion criteria are designed to enroll a sample of Veteran HD patients with some level of executive functioning impairment in order to engage treatment targets. We do not believe this will exclude a significant number of Veterans. In our most recent sample of 55 HD patients over age 60, 73% were impaired on one or more of four DKEFS subtests (Tower, Trail Making, Verbal Fluency, or Color-Word Interference Tests). For the proposed study, patients must demonstrate impaired performance on one or more of the five DKEFS subtests given (Color-Word Interference, Verbal Fluency, Trail Making, Design Fluency, Tower Test). These criteria are optimal in that it will allow for a range of executive functioning within our sample to look at predictors of response as well as allow us to engage this intermediary target.

[figure not shown]

Figure 2. Study Design

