Format and Course of Treatment Given the chronic and severe nature of HD, researchers have found that it requires a relatively lengthy course of treatment¹⁴ (24-26 individual sessions)^{57,70}. Both the control and experimental condition utilizes a 60 minute session-by-session manualized treatment protocol and will take 6 months to complete. Each participant will

months to complete. Each participant will receive 26 sessions of individual treatment. In the experimental condition, patients will receive 7 sessions of CCT and 19 sessions of ET (consisting of exposure to discarding and acquiring modules). In the control condition, patients will receive 26 sessions of ET. The patient and therapist have their own workbook copy for both conditions to follow along during each session (Appendix 1 for CREST and Appendix 2 for ET condition). For the conceptualization of CREST, refer to Figure 3.

Experimental Condition: CREST Compensatory Cognitive Training (CCT) Modules (7 sessions). Compensatory

Cognitive Training^{60,61,62} is a manualized, lowtech, cognitive training intervention designed to target cognitive impairments common in people with psychiatric illness. The original CCT treatment manual has been distributed to over 250 clinicians and has been used with schizophrenia, brain injury, mild cognitive impairment, multiple sclerosis, Parkinson's

[figure not shown]

Figure 3. Conceptualization of CREST

disease, and substance use disorder patients. The CCT modules specifically selected for CREST map onto known areas of HD neurocognitive deficits or weakness and include training in prospective memory, prioritizing, problem solving, planning, and cognitive flexibility. Because habit learning is also highly resistant to forgetting⁷¹, we aimed to help Veteran participants form new habits in executive functioning to automate tasks and reduce the active cognitive effort usually demanded for effective performance. CCT does not use computers, and strategies taught do not "train to the test" or use any of the outcome measures during training. It is believed that using CCT will aide in the implementation of ET exercises. That is, CCT will provide patients with the necessary skills to fully comply with treatment (attendance and homework completion) and tools to prevent relapse.

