Session 8. Exposure preparation	Discussion of expectations, decision making, habituation, and avoidance; rules of discarding; motivational interviewing about willingness to change; acquisition hierarchy; fear of discarding hierarchy			
Session 9. Introduction to exposure therapy	Review of organizational plan, rules of organizing, maintenance system, and rules of discarding; introduction to Subjective Units of Distress (SUDS) Ratings; discarding exposure			
Sessions 10-22: Exposure to discarding & acquiring	Evaluation of progress; discarding exposure; discussion of reasons for saving and strategies for making discarding choices; introduction to advanced exposure (e.g., discussion of rules, preparing for sorting for a longer time and use of outside help); review of treatment goals			
Sessions 23-24: Advanced exposure	Longer exposure time (2-4 hours) with outside help; Evaluation of progress; discussion of reasons for saving and strategies for making discarding choices; review of treatment goals			
Sessions 25-26: Relapse prevention and maintenance	Review of progress in therapy; discussion of everyday uses for cognitive strategies (e.g., calendar use, "to do" lists, problem solving); exposure review; planning for the future			

Table 1. CREST Modules, Target Domains, and Manual Content

Problem solving skills are then taught as HD patients have difficulty finding solutions and taking action towards solving everyday problems. The 6-step approach; Define the problem, Brainstorm solutions to the problem, Evaluate each solution, Select a solution to try, Try the solution, and Evaluate the solution (DBESTE) is reviewed through the use of worksheets. Appropriate planning strategies are then reviewed in conjunction with their new problem solving skills (e.g., You selected to call an exterminator for your roach problem, what steps do you have to take to accomplish this task?). Further, learning how to shift set or change their behaviors

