Power analyses are performed for all hypotheses, incorporating the longitudinal nature of the design. Within this design, repeated observations within subjects are potentially correlated. This has a profound impact on the resulting tests of significance⁹⁸. When the within subject correlation is properly incorporated, the repeated measures analysis takes full advantage of all information obtained from each subject, thereby greatly increasing statistical power over methods that compare treatments cross sectionally⁹⁹. Using the method described by Diggle, Liang, & Zeger¹⁰⁰ and Ahn et al.¹⁰¹, power calculations can be made for repeated measures designs under specified assumptions. Hedeker, Gibbons, & Waternaux¹⁰² extend Diggle et al.¹⁻³'s method for various covariance structures. Procedures describes by Hedeker et al.¹⁰² for Random Regression Models which incorporated these principles was used for the proposed study to estimated needed sample size (RMASS program provided by Hedeker for the Random Regression Model). The design assumptions consist of a 2 treatment groups and up to 7 visits (baseline, sessions 7, 13, 21, 26, and 3- and 6-month follow-up) where the slope is the dependent measure. Other assumptions used were alpha-level, nature of the hypothesis (two-sided versus one-sided), drop-out rate, and variance-covariance matrix of the longitudinal data. We assume a Type-I error level (alpha-level) of .01 to 0.05, drop-out rate of 15% and an autoregressive covariance structure. Data reported in the preliminary studies section which included our own pilot studies were used to calculate effect sizes. From the preliminary analysis of pilot study, the estimated standard deviation (SD) for SI-R score ranges from 12.75-12.82 and the between visit correlation coefficient of 0.71. We considered a range of estimates of stand deviations of 12.5, 12.8 and 13.0, and correlations of .45 to 0.70 in our power analysis. We have reported large effect sizes of 1.02 and 1.51 from our previous studies which converted to differences of 60 to 37 for our primary outcome. However, for these calculations, we conservatively selected smallest clinically meaningful differences that we would like to be able to detect. This was then converted to a medium effect size, defined mathematically as a between-group difference increasing linearly from 0 at baseline to .5 SD units at the last time point. Calculations using the above assumptions indicated that the study will have minimum power of 80% to yield a statistically significant result for a medium effect size with the proposed sample size of 136 patients (68 for each of the two groups).

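### Exploratory Aim 4 asks when the maximum effect occurs, but its planned survival analysis measures time to a >35% SI-R response

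*Combined protocol and SAP*

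**What the plan says.** Under Proposed Study Design, the investigators state that "we will explore outcome moderators (age and baseline executive functioning) and time to maximum effect". The Statistical Plan, under Exploratory Aims 3 and 4, makes the second of these operational as "time to maximum effect of treatment gains (>35% reduction on SI-R) using survival analysis". It plans a Kaplan-Meier curve for each arm and adds: "The parameter estimates and 95% CI for the hazard ratio will be obtained from the Cox proportional hazards". The censoring rule is: "Subjects who do not respond to treatment will be censored on their last visit date".

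The aims are labelled exploratory ("These exploratory aims will be examined using random effects regression analyses for each candidate moderator"), and no event count, hazard ratio or power figure is given for Aim 4.

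The Power Analysis counts "up to 7 visits (baseline, sessions 7, 13, 21, 26, and 3- and 6-month follow-up", and Table 2 lists SI-R at each of them, so there are six post-baseline readings. On treatment content, Format and Course of Treatment says that in CREST "patients will receive 7 sessions of CCT and 19 sessions of ET". Table 1 places exposure preparation in session 8, and the first listed discarding exposure in the next row, "Session 9. Introduction to exposure therapy". The control arm has exposure therapy in all 26 sessions.

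The plan does not say whether a first or a sustained crossing counts, which time scale is used, how ties or interval censoring are handled, or whether proportional hazards will be checked.

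**The concern.** The time at which a patient passes 35% and the time at which that patient has improved most are different quantities. Someone who passes 35% at session 13 and reaches 60% at session 26 has the event at session 13 if the first crossing counts. Someone who improves by 30% at best never has the event, although that patient's best visit is well defined. A report that follows the plan exactly would present time to response under the name of time to maximum effect.

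The choice of model adds to this. A Cox model with one hazard ratio suits finely measured times and a hazard ratio that stays roughly constant. Here the times are seen only at six visits, and the arms receive different content in the first seven sessions, just when the first SI-R follow-up is taken. If the control arm leads early and CREST later, one averaged ratio would not show it.

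**Working it through.** The plan states no figure for Aim 4, so there is none to reproduce. Each part was checked separately.

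**1. Label against endpoint.** The aim concerns the maximum. The event is a fixed threshold, and the censoring rule itself speaks of patients who do not respond. Every patient with follow-up has a visit of largest improvement, but only those above 35% have this event. This needs no outside assumption.

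A simulation shows how far the two can differ. From the Power Analysis: SD 12.8, and a correlation of 0.7 between successive visits with an autoregressive structure. Assumed: baseline mean 60; visits at weeks 0, 7, 13, 21, 26, 39 and 52; mean falls of 17 points (ET) and 23 points (CREST), reached linearly by week 26 and then held. At a baseline of 60 the threshold is 0.35 × 60 = 21 points. Across the scenarios run:
- 54-66% of responders had their largest reduction at a visit other than the first crossing.
- 28-39% of responders were no longer above 35% at the last visit.

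**2. Grouped event times.** The Statistical Plan analyses patients with a baseline and at least one later evaluation, and allows 10% drop-out before that evaluation: 136 × 0.90 = 122.4, about 122. The responder share is assumed to be 40-60%.
- Events: 122 × 0.40 = 49 to 122 × 0.60 = 73.
- Average per visit: 49 / 6 = 8.2 to 73 / 6 = 12.2, so about 8 to 12.
- With the 15% drop-out used in the Power Analysis: 136 × 0.85 = 116 patients, giving 46 to 70 events, or 7.7 to 11.6 per visit.

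The effect of ties on the estimate was checked with a true constant hazard ratio of 1.58 on six visit times:

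| Method | Estimated ratio |
|---|---|
| Cox, Breslow ties | 1.49 |
| Cox, Efron ties | 1.57 |
| Discrete-time complementary log-log | 1.57 |

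**3. Proportional hazards.** In the simulation of step 1, the ratio at visit j is ln(1 − h_CREST,j) / ln(1 − h_ET,j), where h is the share of patients still without response who respond at that visit. Three assumptions about when CREST begins to lower SI-R were compared:

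| CREST effect begins | S7 | S13 | S21 | S26 | 3 mo | 6 mo |
|---|---|---|---|---|---|---|
| After 7 weeks (cognitive training alone has no effect) | 0.31 | 0.89 | 1.58 | 1.77 | 1.53 | 1.46 |
| After 3.5 weeks | 0.79 | 1.25 | 1.64 | 1.69 | 1.46 | 1.46 |
| At once | 1.46 | 1.54 | 1.65 | 1.63 | 1.46 | 1.46 |

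Under the first row, a single Cox ratio comes out at 1.32 (Breslow) or 1.39 (Efron). The simulated responder share is about 70% (some 95 events among 136 patients, without drop-out), above the range in step 2. The table therefore illustrates the pattern and is not a forecast.

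**The case against.** The strongest reply is that much of the trouble is conditional or already covered.

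- **Proportional hazards.** A reader might infer that the design itself breaks proportional hazards, so that the ratio must change over time. The documents do not support that. It follows only if cognitive training alone leaves SI-R nearly unchanged, and they never say so. The plan calls exposure the true mechanism of symptom change, which points towards a delay. But the CREST modules also teach organising and home-maintenance routines with daily homework, and SI-R has a clutter subscale. With no delay the ratios are close to constant.
- **Interpretability.** A reader might also conclude that the hazard ratio would be uninterpretable. That goes too far. The Kaplan-Meier curves already planned need no proportionality and would show a crossing. Even under full delay the averaged ratio has the same direction as four of the six visit ratios.
- **Ties.** Ties alone do not invalidate a Cox model: Efron's method does as well as the discrete-time model. The reference to a last visit date suggests that calendar dates may be used, which would reduce exact ties, though the interval censoring would remain.
- **Exposure count.** It is tempting to say that control patients have had seven exposures by session 7. The session content of the control manual is not in the text, so that count is an inference.
- **First crossing.** Reading the event as the first crossing is natural in survival analysis, but the plan does not say so.
- **Importance.** The aim is exploratory, and neither the primary analysis nor the sample size depends on it.

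All of this stands. None of it touches the central mismatch: a threshold for response does not measure when the effect is greatest.

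**Conclusion.** The concern holds in a limited form. As written, Aim 4 is not answered by its own analysis, and this rests on the text alone. That event times are interval-censored follows from the visit schedule. The density of ties, about 8 to 12 per visit, rests on the assumed 40-60% responder share and on nominal visit times, and the resulting bias is small if a suitable tie method is used. Proportional hazards is doubtful and no check is planned. It fails clearly if cognitive training alone changes SI-R little, and then a single hazard ratio of about 1.3 to 1.4 would hide an early lead for the control arm. The stronger conclusions, that proportional hazards fails by design or that the hazard ratio would have no meaning, are not supported. This is a worthwhile refinement of an exploratory aim; no confirmatory result is at risk.

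**What to change.** 1. Rename the endpoint *time to first >35% SI-R reduction*, which also settles whether a first or a sustained crossing counts.
2. Analyse it with a discrete-time complementary log-log model with visit as a factor. Test a group-by-visit term, pooling sparse early visits if few CREST patients have responded by session 7. Report the proportion responding by visit beside the Kaplan-Meier curves.
3. Address time to maximum effect descriptively from the saturated treatment-by-time mixed model already in the Statistical Plan. Give mean SI-R improvement by visit and arm with confidence intervals, and name the visit of largest mean gain. State that this is a group-level quantity, not a patient's own time to maximum, and that it may be imprecise if the late means plateau.

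No new data, visits or patients are needed. The cost is a little more analysis work and, if the group-by-visit term is kept, no single hazard ratio to report.
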